4.2. Inclusion Criteria

Subjects must satisfy the following criteria to be enrolled in the study:

- 1. Subject must be ≥ 18 years and ≤ 75 years of age and have a body weight of ≥ 40 kg (88.2 lb) at the time of signing the informed consent form (ICF). Subjects in Japan must also be of legal age of consent (≥ 20 years of age) at the time of signing the ICF.
- 2. Subject has chronic AD as defined by Hanifin and Rajka (Appendix B) that has been present for ≥ 1 year prior to the baseline visit (Day 1).
- 3. Subject has moderate to severe, active, and symptomatic AD defined by meeting all of the following criteria on the day of the baseline visit (Day 1):
 - a. Body Surface Area (BSA) \geq 10%, and
 - b. EASI score ≥ 16 , and
 - c. $vIGA-AD \ge 3$, and
 - d. Pruritus NRS severity score ≥ 4 .
- 4. Subject must have a documented history of inadequate response to treatment with topical medications for at least 4 weeks, unless topical treatments are otherwise medically inadvisable (eg, because of important side effects, safety risks, and/or previous intolerance), or has required systemic therapy for control of disease.

Inadequate response is defined as either or both of:

- a. failure to achieve and/or maintain a disease activity state comparable to IGA 0 [clear] to 2 [mild], despite treatment with a daily regimen of TCS of medium to higher potency (± TCI as appropriate), applied for at least 4 weeks (28 days) or for the maximum duration recommended by the product prescribing information, whichever was shorter, OR
- b. necessity of systemic therapy to control disease.
- 5. Subject must be willing to apply a stable dose of topical emollient (eg, over-the-counter moisturizer, non-medicated emollient, etc.) twice daily for \geq 7 days prior to the Baseline visit and continue application throughout the study. Refer to Section 8.3 for additional requirements related to application of topical emollient throughout the study.
- 6. Subject must commit to avoid prolonged exposure to the sun and not to use tanning booths, sun lamps or other ultraviolet light sources during the study.

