9.3. Sample Size and Power Considerations

Approximately 200 subjects will be randomized in this Phase 2 dose ranging study. Randomization will be equal among the 4 dose groups of placebo, mg Q2W, mg Q2W, and mg QW (approximately 50 subjects per group). Assuming a 10% dropout rate, a sample size of 45 subjects per group will provide approximately 90% power to detect a treatment difference relative to placebo (difference in means) of 35% with respect to the primary endpoint of percentage change from baseline in EASI scores at Week 16. In these power calculations superiority over placebo for a particular dose group is met if the lower bound of the (2-sided) 95% confidence interval (z-score) for the treatment difference exceeds zero (adjusted for multiplicity).

The sample size calculations are based on the following considerations for comparing mean percentage changes from baseline in EASI scores at Week 16 versus placebo. In particular, the recent Phase 2b study of dupilumab reported an observed mean for placebo of 18.1% and corresponding treatment differences of 50.1% (standard error [SE = 6.7%]) and 55.7% (SE = 6.7%), for the doses of 300 mg Q2W, and 300 mg QW, respectively (Thaci, 2016). This study evaluating CC-93538 is designed to detect a (true) treatment difference relative to placebo of 35%. We assume a (true) mean of 20% for placebo, and means for the active dose groups corresponding to treatment differences of 25% mg Q2W), 30% mg O2W), and 35%mg QW), with a common standard deviation (SD) of 50%. We note that the common SD assumption of 50% for the percentage change from baseline in EASI scores at Week 16 was also assumed in the dupilumab Phase 2b study design (Thaci, 2016). Under these assumptions, it is estimated that with a sample size of 45 subjects per group the study provides approximately 90% power to detect superiority relative to placebo for at least 1 dose at the overall type-1 error of α = 0.05 (two-sided) using a hierarchical testing approach (in the order of mg QW versus placebo. mg Q2W versus placebo, and mg Q2W versus placebo).

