9.6.2. Efficacy Analysis of Secondary Endpoints

9.6.2.1. Analysis Methods

For the first key secondary endpoint of proportion of subjects with both a vIGA-AD score of 0 (clear) or 1 (almost clear) and a reduction of 2 or more points in vIGA-AD score from Baseline at Week 16 will be analyzed based on the mITT population using a stratified Cochran-Mantel-CMH test at a two-sided 5% significance level. The randomization stratification levels are: (1) Japan region, (2) RoW region and vIGA-AD score 3, and (3) RoW region and vIGA-AD score 4. Estimates of the differences in proportions between each treatment group versus placebo, and associated 95% confidence intervals will be provided along with p-values. Missing endpoint values (eg, due to study dropout or other reasons for lack of assessment) will be imputed as non-responders. A sensitivity analysis will be conducted based on defining subjects who initiate rescue therapy (prior to Week 16) as missing and treated as non-responders.

The second key secondary endpoint of proportion of subjects with at least a 75% improvement from baseline in Eczema Area and Severity Index (EASI-75) at Week 16 will be analyzed in the same manner as above.

The hierarchical testing approach used for the primary endpoint will be utilized to adjust for multiplicity with respect to the 3 active doses for each of these key secondary endpoints. However, multiplicity adjustments are not implemented across the primary and 2 key secondary endpoints simultaneously.

The following endpoints will be analyzed in the same manner as the key secondary endpoints, excepting that p-values will not be provided:

- The secondary endpoint of proportion of subjects with Pruritus NRS change of ≥ 4 from Baseline at Week 16
- The secondary endpoint of proportion of subjects with a 90% improvement from Baseline in EASI (EASI-90) at Week 16

The following endpoints will be analyzed in the same manner as the primary endpoint, excepting that p-values will not be provided:

- The secondary endpoint of percentage change from baseline in Pruritus NRS at Week 16
- The secondary endpoint of percent change in SCORAD Scores from Baseline at Week 16

• The secondary endpoint of mean percent change in Body Surface Area (BSA) involved with AD from Baseline at Week 16

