For the secondary endpoint of time to achieve at least 4 points of improvement in the severity of pruritus NRS scale in the first 16 weeks of treatment, the distribution of times to the first event of 4-point improvement will be compared based on Kaplan-Meier (K-M) and log-rank approaches. Comparisons versus placebo, for each dose group separately, will be based on a stratified log-rank test with associated p-value provided. The stratification levels are: (1) Japan region, (2) RoW region and IGA score 3, and (3) RoW region and vIGA-AD score 4. The K-M estimates for the cumulative proportions of subjects achieving a 4-point improvement, by specific timepoints, will be provided by dose group as well as differences with placebo and associated 95% confidence intervals. These will be reported at various timepoints (eg, Day 1 to 28, followed by weekly assessments). Censoring rules will be described in the SAP.

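### The itch-onset log-rank and the Week 16 4-point itch responder estimate leave out Day 1 Pruritus NRS; both are valid but probably somewhat inefficient

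*Combined protocol and SAP*

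**What the plan says.** For itch onset, Section 9.6.2.1 specifies Kaplan-Meier estimates and, for each dose against placebo, a stratified log-rank test with a p-value. The strata are fixed in the text: "The stratification levels are: (1) Japan region, (2) RoW region and IGA score 3, and (3) RoW region and vIGA-AD score 4". Only the censoring rules are left to the SAP.

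The same section lists "The secondary endpoint of proportion of subjects with Pruritus NRS change of" at least 4 points at Week 16 among the endpoints handled like the key secondary ones. It therefore has the same three strata and a difference in proportions with a confidence interval, but no p-value.

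Inclusion criterion 3d (Section 4.2) requires a "Pruritus NRS severity score" of at least 4 on Day 1. Table 4, footnote h, makes the pre-dose Day 1 score the one used for eligibility, and Section 6.5.1 gives the scale as 0 to 10. Every randomised subject should therefore have a Day 1 score between 4 and 10.

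The primary EASI model (Section 9.6.1.1) does adjust for the baseline value of its own measure. Percentage change in Pruritus NRS is to be analysed in the same way as the primary endpoint.

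**The concern.** The event is a fixed drop in points, so the proportional improvement it demands depends on where the subject starts. vIGA-AD grades skin signs, not itch, and it is a stratification level only outside Japan. The three strata may therefore carry little information about starting itch.

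Leaving out a prognostic baseline has two costs. A log-rank comparison loses some power, and chance imbalance in baseline itch between arms of about 50 stays in both itch estimates. Itch onset is also the only non-key secondary efficacy endpoint for which the plan promises a p-value. The remedy needs no new data.

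**Working it through.** **1. The plan's own figures.** The stated power concerns EASI and vIGA-AD only. Section 9.3 says that "a sample size of 45 subjects per group will provide approximately 90% power"; the study "is designed to detect a (true) treatment difference relative to placebo of 35" percentage points, "with a common standard deviation (SD) of 50"%, "at the overall type-1 error of α = 0.05 (two-sided) using a hierarchical testing approach".
- SE of the difference = 50 × √(2/45) = 10.54. Then 35/10.54 − 1.96 = 1.36, so power = Φ(1.36) = 0.913 (0.907 with the noncentral t). The stated 90% reproduces.
- "Assuming a 10% dropout rate": 45/0.90 = 50 per arm.
- vIGA-AD, 2% against 25%, 45 per arm: 0.905. The stated figure of more than 90% reproduces.

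Neither itch endpoint has a stated power, event count, effect size or baseline distribution. Everything after step 2 therefore rests on assumed itch inputs.

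**2. Why Day 1 NRS should predict the event.** The proportional reduction needed is 4 divided by the Day 1 score:
- score 4: 4/4 = 100%
- score 5: 4/5 = 80%
- score 7: 4/7 = 57%
- score 10: 4/10 = 40%

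In one simulation on the plan's assessment schedule, this threshold alone produced a log hazard ratio of about 0.30 per NRS point; it was not imposed. Simulated placebo subjects with any 4-point event rose from 12% at a Day 1 score of 4 to about 60% at 9-10.

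**3. Itch onset: power of the planned log-rank against a Cox model with the same three strata plus continuous Day 1 NRS.** All runs used two-sided 0.05. The first two settings had 50 per arm.

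| Assumed setting | Planned log-rank | Cox with Day 1 NRS | Gain (points) |
|---|---|---|---|
| Day 1 NRS mean 7.1, SD 1.6; itch reduction 22% vs 42%; day-to-day SD 1.0 | 0.66 | 0.74 | 8 |
| Same, day-to-day SD 1.5 | 0.34 | 0.47 | 13 |
| 22% vs 42%, with 10% dropout and between-subject variation in response; day-to-day SD 1.0 | 0.55 | 0.61 | 6 |
| Same, day-to-day SD 1.5 | 0.30 | 0.41 | 11 |
| 15% vs 35%, otherwise as above; day-to-day SD 1.0 | 0.56 | 0.59 | 3 |
| Separate runs of the Cox score test, including two low-event scenarios | not listed | not listed | 1 to 7 |

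Rejection rates under the null were 0.042 to 0.056. Monte Carlo error is about 2 to 2.5 points in the runs of 400 to 500 trials.

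A further set imposed the prognostic strength directly, with 50 per arm, 16 weekly looks and 10% dropout. Event rates by Week 16 were 27.3% vs 50% or 10% vs 25%. The placebo rates are close to the 27.3% and 10.3% that Section 1.3.1 reports for other agents; the active rates are assumed. The planned log-rank had power 0.62-0.68 and 0.48-0.52. The gain of Cox with Day 1 NRS over the same Cox without it was:
- log hazard ratio 0.15 per point: 0 to 2 points
- 0.3: 2 to 4 points
- 0.5: 3 to 12 points
- 0.7: 19 points (one scenario)

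Against the planned log-rank, the adjusted Cox model in this set ranged from −5 to +17 points, with the lower values at 10% vs 25%. Some sparse fits gave convergence warnings.

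**4. Adding NRS categories to the log-rank strata.** Three strata by three NRS categories make 9 cells for about 100 subjects per comparison, or about 11 per cell. With imposed prognostic strength, power changed by −5 to −2 points for no effect, −2 to +1 at 0.3, and −2 to +6 at 0.5. In a model with between-subject variation in response, nine cells moved power from 0.66 to 0.67 and from 0.36 to 0.35. Gains up to 11 points appeared only when subjects did not vary in response.

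**5. Week 16 responders.** The simulated variance of the risk difference fell by 2-12%. The SE therefore falls by 1 − √0.98 = 1% to 1 − √0.88 = 6%. This is equivalent to 1/0.98 = 1.02 to 1/0.88 = 1.14 times the sample, or 2% to 14% more patients.

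**The case against.** The strongest reply is that nothing is broken. The planned test follows the randomisation strata and holds its size. Both endpoints are non-key secondary endpoints in a Phase 2 dose-ranging study, and itch onset lies outside the testing hierarchy, so its p-value is nominal. Itch is also analysed as a percentage change, which scales each subject to their own baseline. A Cox hazard ratio adds a proportional-hazards assumption and is conditional on baseline, whereas the planned Kaplan-Meier differences are marginal. With few events, it did not beat the log-rank in every run. All of this stands. It limits the weight of the point but does not remove it.

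A reader might go further and infer that starting itch largely decides who responds. The documents do not support that. The entry floor of 4 lets every subject achieve a 4-point drop, no section links baseline itch to response, and in the models run it explained only about 2-15% of within-arm responder variation.

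A reader might also infer that both endpoints lose power. The Week 16 endpoint has no test, so only precision is at issue there.

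Deferral to the SAP (Section 9.1) does not answer the point. Section 9.6.2.1 sets the strata itself, and the documents provided contain no SAP text that changes them.

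**Conclusion.** The point holds as a modest, low-cost efficiency improvement. Day 1 NRS is in neither 4-point itch analysis, although it is available before dosing and likely to be prognostic.

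For itch onset, a reasonable working range is a gain of about 0 to 10 power points. It is near zero if baseline itch is weakly prognostic, and individual scenarios fall outside the range on both sides. For Week 16, the variance falls by roughly 2-12%. Both ranges rest on assumed itch distributions, noise, effect sizes and prognostic strength, and cannot be derived from the documents. Primary and key secondary conclusions are unaffected.

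**What to change.** Amend Section 9.6.2.1 before unblinding:

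1. **Itch onset.** Base the comparison with placebo on the score test from a Cox model with the same three strata, treatment and continuous Day 1 Pruritus NRS, and report the hazard ratio. Keep the planned log-rank and Kaplan-Meier differences as supportive.
2. **Week 16 4-point responders.** Adjust the risk difference for both the three randomisation strata and continuous Day 1 NRS, for example as a standardised risk difference from a logistic model. Keep the non-responder rule for missing values.

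Do not cross NRS categories with the three strata in the log-rank, and do not drop the randomisation strata from either analysis.

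The cost is a wording change, a little more analysis work and a proportional-hazards working model for the hazard ratio. No new data or subjects are needed.

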9.7. Safety Analysis

All analyses of safety data will be conducted using the Safety population by treatment for the entire study duration of 32 weeks. The assessment of safety will include AEs, SAEs, AEs leading to discontinuation of study treatment, and AEs leading to discontinuation from the study; changes from baseline in laboratory values and vital signs; and incidence and type of laboratory, vital signs, and physical examination abnormalities. Individual data listings will also be provided.

Adverse events will be monitored during the trial, and the data will be summarized by worst severity grade. Adverse events, with focus on treatment-emergent AEs, will be summarized by Medical Dictionary for Regulatory Activities (MedDRA) system organ class, and preferred term. Investigational product-related AEs, AEs leading to death or to discontinuation from treatment, events assessed as moderate or severe, IP-related events, and SAEs, and events of interest.

Laboratory assessments will be performed by a central laboratory. All summaries will be based on the Standard International System of Units (SI) provided by the central lab. Each subject's hematology, blood chemistry, and urinalysis values will be flagged as "low", "normal", or "high" relative to the normal ranges of the central laboratory.

Summary statistics of actual values and changes from baseline in vital signs will be provided by visit.

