Tralokinumab when dosed at 300 mg every other week (Q2W) demonstrated superiority over placebo in all primary and secondary endpoints at Week 16. For the primary endpoint, an IGA 0/1 was achieved for subjects treated with tralokinumab was 15.8% for versus 7.1% for placebo in ECZTRA 1 and 22.2% versus 10.9% for ECZTRA 2. Reduction of the worst daily average of Pruritus Numeric Rating Scale (NRS) \geq 4 from baseline to Week 16 was 20.0% with tralokinumab versus 10.3% with placebo in ECZTRA 1 and by 25.0% versus 9.5% with placebo in ECZTRA 2. The overall frequency and severity of AEs over 16 weeks was comparable between tralokinumab and placebo. Of the most frequently reported AEs (\geq 5% in any treatment group), upper respiratory tract infection and conjunctivitis occurred more frequently with tralokinumab versus placebo, and dermatitis atopic and skin infection occurred more frequently with placebo (Wollenberg, 2020). Tralokinumab demonstrated in Phase 3 studies that targeting IL-13 alone in is both a safe and effective therapy; however, is the overall efficacy profile does not appear to be superior to biologic agents already on the market. When compared to the results

reported from dupilumab Phase 3 SOLO 1 and SOLO 2 induction studies, response rates for achieving IGA 0/1were as high as 38% to 36% in the dupilumab 300 mg Q2W arm, compared to 10% to 8% in subjects treated with placebo (Simpson, 2016). Although tralokinumab is anticipated to the first anti-IL-13 approved for the treatment of moderate to severe AD, there remains a need to further evaluate other biologic agents targeting IL-13 pathway, to further assess anti-IL-13's potential of achieving an optimized efficacy profile in subjects with moderate to severe AD.

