Although concurrent treatment with background therapy to alleviate AD symptoms is prohibited during the Treatment and Follow Up periods of the study, the use of rescue medication, described in Section 8.4, may be employed for subjects who experience intolerable AD symptoms after randomization.

The maximum duration of subject participation in this study is approximately 36 weeks. Subjects will participate up to 4 weeks in the Screening Period. Subjects will participate in a Screening Period that lasts up to 4 weeks. Over the treatment period, subjects will receive a total of 16 doses IP, administered QW, starting at Day 1/ Week 0 and ending at Week 15. At Week 16, subjects will return for the End of Treatment Visit for safety and efficacy assessments. Following the Week 16 End of Treatment Visit, subjects will enter a 16 Week Follow Up Period, and will return for 2 additional visits to assess safety, clinical status, PK/PD, and serum antibodies to CC-93538.

The Initial Follow Up Visit will be conducted 8 weeks after the End of Treatment Visit (Week 24) and the Final Follow Up/End of Study Visit will be conducted 16 weeks after the End of Treatment Visit (Week 32).

The blind should be maintained for persons responsible for the ongoing conduct of the study until after the primary analysis database lock, that is projected to be initiated after all subjects have completed Week 16/End of Treatment Visit assessments. Blinded persons may include but are not limited to: Clinical Research Physician, Clinical Research Scientist, Clinical Trial Manager, Study Statistician, Data Manager, Programmers, Clinical Research Associates.

The study will be conducted in compliance with the International Council on Harmonisation (ICH) of Technical Requirements for Registration of Pharmaceuticals for Human Use/Good Clinical Practice (GCP) and applicable regulatory requirements.

Figure 1: Overall Study Design

Wk= Week(s), EOT =End of Treatment, EOS=End of Study

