7.2.6. Criteria for Discontinuation of Dosing

Dosing will be required to be permanently discontinued (treatment discontinuation) for a subject if the subject experiences any of the events listed below following initiation of IP.

• SAE which is suspected of being related to IP, and study treatment continuation could present an unreasonable risk to the subject as determined by the Investigator, or Sponsor.

- Experiences a severe or serious (per Investigator assessment) opportunistic infection (suggestive of subject being immunocompromised)
- Receives a malignancy diagnosis, excluding carcinoma in situ of the cervix or squamous or basal cell carcinoma of the skin if it can be successfully treated by local resection
- Experiences an anaphylactic reaction or other severe systemic reaction (eg, hypersensitivity, allergic, or autoimmune) suspected of being related to IP by the Investigator or the Sponsor

- Experiences 2 separate occurrences of severe injection site reactions (ISR) that last longer than 24 hours.
 - A severe ISR is defined as an ISR that manifests with symptoms causing severe discomfort/pain; symptoms requiring medical/surgical attention/intervention; interference with activities of daily life (ADLs) including inability to perform daily social and functional activities (eg, absenteeism and/or bed rest); and/or when drug therapy is required
- Becomes pregnant
- Uses prohibited systemic immunosuppressive or immunomodulating drugs
- Uses systemic rescue therapy
- Misses 3 or more consecutive doses

These subjects will be encouraged to remain in the study and complete all required study assessments (which the exception of dosing with IP) remaining in the treatment period and follow up period of the study. In order to prevent missing data, the site staff will ensure attempts are made to reach subjects by phone or email that do not maintain contact with the Investigator. Any subject discontinuing the study prematurely will be asked to complete the ET Visit and the Initial and the Final Follow-up Visits.

Additional events that are considered sufficient reasons for discontinuing a subject from the IP are summarized in Section 11.1.

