8.4. Rescue Medication

In the event a subject develops intolerable AD symptoms that requires rescue therapy, exceptions related to prohibited medications, such as TCS use, will be permitted. The use of rescue therapy should be discouraged throughout the treatment phase of trial, and reserved for only severe symptoms associated with AD flares. In such cases, subjects may continue study participation, while continuing concomitant rescue therapy use; however, discontinuation of IP may be required depending on the type of rescue medication that is administered.

- Subjects requiring rescue therapy should consider the addition of TCS prior to considering systemic treatment. Any subject who requires TCS rescue therapy treatment are encouraged to continue the TCS for as brief a period as possible (eg less than 7 days), while continuing with treatment with IP, and maintaining the study visit schedule.
- Any subject requiring systemic rescue therapy to treat their AD during the treatment phase of the study will be discontinued from IP and will be encouraged to continue participation in the study without IP administration. Subjects who decline further participation in the study should proceed with the Early Termination Visit and follow up visit assessments. Subjects requiring systemic rescue therapy during the follow up period of the study should continue the study visits as planned. All instances of rescue therapy administration that occur during the course of study participation will be captured accordingly within the source documentation in the eCRF.

The impact of rescue therapy will also be evaluated by defining these endpoints as missing for subjects who initiate rescue therapy prior to Week 16 and analyzed according to methods described in Section 9.

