10. ADVERSE EVENTS

10.1. Monitoring, Recording and Reporting of Adverse Events

An AE is any noxious, unintended, or untoward medical occurrence that may appear or worsen in a subject during the course of a study. It may be a new intercurrent illness, a worsening concomitant illness, an injury, or any concomitant impairment of the subject's health, including laboratory test values (as specified by the criteria in Section 10.3), regardless of etiology. Any worsening (ie, any clinically significant adverse change in the frequency or intensity of a preexisting condition) should be considered an AE. A diagnosis or syndrome should be recorded on the AE page of the CRF rather than the individual signs or symptoms of the diagnosis or syndrome.

Abuse, withdrawal, sensitivity or toxicity to an investigational product should be reported as an AE. Overdose, accidental or intentional, whether or not it is associated with an AE should be reported on the overdose CRF. (See Section 7.2.3 for the definition of overdose). Any sequela of an accidental or intentional overdose of an investigational product which meets the definition of an adverse event, should be reported as an AE on the CRF. If the sequela of an overdose meets serious criteria, then it must be marked as serious on the CRF. The overdose itself should not be reported as an AE.

In the event of overdose, the subject should be monitored as appropriate and should receive supportive measures as necessary. There is no known specific antidote for CC-93538 overdose. Actual treatment should depend on the severity of the clinical situation and the judgment and experience of the treating physician.

All subjects will be monitored for AEs during the study. Assessments may include monitoring of any or all of the following parameters: the subject's clinical symptoms, laboratory, pathological, radiological or surgical findings, physical examination findings, or findings from other tests and/or procedures.

All AEs will be recorded by the Investigator from the time the subject signs informed consent until 16 weeks after the last dose of IP, or the last Follow Up visit, whichever is longer, as well as those SAEs made known to the Investigator at any time thereafter that are suspected of being related to IP. All AEs (serious/non-serious) will be recorded on the CRF and in the subject's source documents. Refer to Section 10.5 for instructions on how to report SAEs to Drug Safety.

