11. DISCONTINUATIONS

11.1. Treatment Discontinuation

The following events are considered sufficient reasons for permanently discontinuing a subject from the IP:

- Adverse event
- Physician decision
- Lack of efficacy
- Protocol deviation
- Withdrawal by subject
- Death
- Lost to follow-up
- Non-compliance with IP
- Other (to be specified on the eCRF)

Subjects who are permanently discontinued from IP will be encouraged to continue participation in the study without IP administration in order to complete all remaining required study assessments including efficacy evaluations. Subjects who decline further participation in the study should complete the early termination visit, and follow up visit assessments. Subjects who discontinue early from IP and/or study participation will not be replaced.

The reason for discontinuation of treatment should be recorded in the CRF and in the source documents.

The decision to discontinue a subject from treatment remains the responsibility of the treating physician, which will not be delayed or refused by the Sponsor. However, prior to discontinuing a subject, the Investigator may contact the Medical Monitor and forward appropriate supporting documents for review and discussion.

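### Section 9.7 plans no AE total that sets worsening of atopic dermatitis apart, so the headline safety rows can move with efficacy and may mask or distort a difference in other AEs

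*Combined protocol and SAP*

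**What the plan says.** - **AE definition (Section 10.1).** "Any worsening (ie, any clinically significant adverse change in the frequency or intensity of a preexisting condition) should be considered an AE". AD is not exempted.
- **Planned safety output (Section 9.7).** "The assessment of safety will include AEs, SAEs, AEs leading to discontinuation of study treatment, and AEs leading to discontinuation from the study". The section also covers moderate or severe events, IP-related events, events of interest, summaries by system organ class and preferred term, and individual listings, all over the 32-week study. It names no total that excludes AD worsening.
- **Rescue and stopping of IP (Sections 7.2.6 and 8.4).** The criteria for permanent discontinuation of dosing include "Uses systemic rescue therapy". Section 8.4 agrees: "Any subject requiring systemic rescue therapy to treat their AD during the treatment phase of the study will be discontinued from IP". Topical corticosteroid rescue is to be considered first and given briefly "while continuing with treatment with IP, and maintaining the study visit schedule".
- **Reason for stopping (Sections 11.1, 11.2 and 10.2.5).** Section 11.1 lists "Lack of efficacy" as a reason separate from an adverse event. Section 11.2, on leaving the study, has no such reason. Section 10.2.5 has the investigator record what was done with IP as a result of each AE.
- **Setting (Sections 3.1 and 1.3.1).** "concurrent treatment with background therapy to alleviate AD symptoms is prohibited during the Treatment and Follow Up periods of the study". For another IL-13 antibody the protocol reports that "dermatitis atopic and skin infection occurred more frequently with placebo".

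**The concern.** An AD flare is both a sign that treatment is not working and, under Section 10.1, an AE. If the drug works, flares should be fewer on active treatment, at least while subjects are dosed. A row that counts subjects with any event then adds an efficacy difference to whatever difference exists in other events, and the two can cancel.

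Flares that need rescue are likely to be graded moderate or severe, because Section 8.4 reserves rescue for severe symptoms and the upper grades in Section 10.2.2 refer to drug therapy. A flare treated with systemic rescue also ends dosing. It can therefore appear as an AE leading to treatment discontinuation if the site records it that way.

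Safety and tolerability of the three regimens against placebo is a secondary objective, and Section 6.6 describes this as the first study at higher cumulative exposures. The aggregate rows are what most readers compare first.

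**Working it through.** **What the documents supply.** They give the counting rule and the direction seen with a similar antibody. They give no rate for TEAEs, AD worsening or rescue in this trial, so there is no figure on this point to reproduce. All rates below are assumptions. They show how the rows behave and do not predict results.

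**Formula.** If AD worsening and other events are independent within an arm, the proportion with any event is 1 - (1 - AD)(1 - other).

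**Any TEAE.** Other TEAEs are assumed at 45% placebo and 55% active, a true difference of +10 points.

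| AD worsening, placebo v active | Placebo total | Active total | Shown difference (points) |
|---|---|---|---|
| 10% v 5% | 1 - 0.90 × 0.55 = 50.5% | 1 - 0.95 × 0.45 = 57.25% | +6.75 |
| 15% v 5% | 1 - 0.85 × 0.55 = 53.25% | 57.25% | +4.0 |
| 25% v 7.5% | 1 - 0.75 × 0.55 = 58.75% | 1 - 0.925 × 0.45 = 58.375% | -0.375 |
| 35% v 10% | 1 - 0.65 × 0.55 = 64.25% | 1 - 0.90 × 0.45 = 59.5% | -4.75 |

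**Other base rates, same +10 points.** For AD worsening of 10% v 5%, 15% v 5%, 20% v 5% and 25% v 8%, the shown difference is +6.5, +3.5, +0.5 and -1.0 with other TEAEs at 40% v 50%. It is +7.0, +4.5, +2.0 and +0.7 at 50% v 60%.

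**Independence.** Take the 25% v 7.5% row. If every subject with a flare also has another TEAE, the totals stay at 45% and 55% (+10). If no subject has both, they are 45 + 25 = 70% and 55 + 7.5 = 62.5% (-7.5). Independence lies between these.

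**TEAEs leading to stopping IP.** Non-AD stops are assumed at 2% placebo and 6% active, a true +4 points. Every flare-driven stop is counted as an AE stop.

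| Flare stops, placebo v active | Placebo total | Active total | Shown difference (points) |
|---|---|---|---|
| 3% v 1% | 1 - 0.97 × 0.98 = 4.9% | 1 - 0.99 × 0.94 = 6.9% | +2.0 |
| 5% v 1% | 1 - 0.95 × 0.98 = 6.9% | 6.9% | 0.0 |
| 8% v 2% | 1 - 0.92 × 0.98 = 9.8% | 1 - 0.98 × 0.94 = 7.9% | -2.0 |
| 10% v 2% | 1 - 0.90 × 0.98 = 11.8% | 7.9% | -3.9 |

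If sites record these stops as lack of efficacy and not as the action taken for an AE, the row keeps the assumed +4 points.

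**Scale.** With about 50 per arm, 2% v 6% is 1 v 3 subjects, and the standard error of that difference is √(0.02 × 0.98/50 + 0.06 × 0.94/50) = 3.9 points. For 45% v 55% it is √(2 × 0.45 × 0.55/50) = 9.9 points.

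**The case against.** A reader might infer that placebo AE totals and AE discontinuations will be raised by lack of efficacy, and that drug harm will be hidden. The documents do not support that, for these reasons.

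- **Coding.** Section 11.1 has a separate lack-of-efficacy reason, and systemic rescue is a stopping criterion in its own right. A flare enters the AE-discontinuation row only if the site records the stop as the action taken for that AE. No section says which applies. This stands: the effect on that row is conditional.
- **Topical rescue.** It comes first and does not stop IP, which limits forced stops. This stands for discontinuations. A flare treated topically is still an AE in the other rows.
- **Worsening is more than non-response.** A subject who stays at baseline severity has no AE, and Section 9.3 assumes a placebo mean of 20% on the EASI scale in the direction of improvement. This stands: only clinically significant worsening counts.
- **Other outputs.** Preferred-term tables, IP-related summaries and listings would show non-AD harm. This stands at term level. However, preferred-term rows cannot be subtracted to give a subject-level total, because one subject can have several events. Rebuilding the total from listings after unblinding would be post hoc.
- **Time window.** The 32 weeks include 16 weeks of follow-up after treatment, when active-arm subjects may flare too. The net direction over the whole study is therefore not fixed. This stands, and it is a further reason to separate these events.
- **Small numbers and deferred detail.** Safety is described and not tested, the assumed differences are no larger than about one standard error, and Section 9.1 leaves further detail to the SAP. All true. This keeps the point minor and shows where the change can be made.

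**Conclusion.** The point holds in a limited form. Because worsening of AD is an AE and Section 9.7 plans no total without it, the any-TEAE and moderate-or-severe rows can be shifted by differences in flares between arms. TEAEs leading to discontinuation can be shifted too, depending on coding. These rows may then mask or distort a difference in other AEs. The documents do not establish that harm would be hidden or that AE discontinuations will be higher on placebo.

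The size cannot be derived. Across the assumed rates and under independence, a true +10 points in TEAEs is shown as anything from +7.0 to -4.75. A true +4 points in AE stops is shown as +2.0 to -3.9 if flare stops are coded as AEs, and is unchanged if they are not. More overlap between flares and other events in the same subjects would weaken the effect. Severity is minor.

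**What to change.** In Section 9.7 or the SAP, before unblinding, add subject-level totals by arm for any TEAE, moderate or severe TEAEs, SAEs, and TEAEs leading to treatment or study discontinuation. Show each one twice: for all events, and excluding a pre-specified list of AD-worsening preferred terms. A subject with both a flare and another event stays in the second total on account of the other event.

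Keep the all-events rows, since worsening of AD on or after treatment is itself of interest. The second discontinuation row does not depend on how sites code flare-driven stops, provided the list captures the terms used: a flare coded as an AE is removed, and one coded as lack of efficacy was never counted.

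AE reporting, rescue and stopping rules, endpoints and sample size are unchanged. The cost is a short term list and a few table rows. The drawback is having two sets of totals to explain.
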